8.6.2 Definition of Treatment-Emergent Adverse Event

A TEAE is any condition that was not present prior to treatment with the IP but appeared following treatment, was present at treatment initiation but worsened during treatment, or was present at treatment initiation but resolved and then reappeared while the individual was on treatment (regardless of the intensity of the AE when the treatment was initiated).

8.6.3 Definition of Serious Adverse Event

A SAE or reaction is any untoward medical occurrence that, at any dose has any of the following consequences:

- Results in death
- Is life-threatening
- Requires in-patient hospitalization or prolongation of existing hospitalization
- Results in persistent or significant disability/incapacity
- Is a congenital anomaly/birth defect

Note: The term "life-threatening" in the definition of "serious" refers to an event in which the participant was at risk of death at the time of the event; it does not refer to an event that hypothetically might have caused death if it were more severe.

Medical and scientific judgment should be exercised in deciding whether expedited reporting is appropriate in other situations, such as important medical events that may not be immediately life-threatening or result in death or hospitalization, but may jeopardize the participant or may require intervention to prevent one of the other outcomes listed in the definition above. These should also usually be considered serious.

Important medical events that may not result in death, be life-threatening, or require hospitalization may be considered serious when, based upon appropriate medical judgment, they may jeopardize the participant or participant and may require medical or surgical intervention to prevent one of the outcomes listed in this definition. Examples of such medical events include allergic bronchospasm requiring intensive treatment in an emergency room or at home, blood dyscrasias or convulsions that do not result in inpatient hospitalization, or the development of drug dependency or drug abuse.

8.6.4 Definition of an Adverse Event of Special Interest (AESI)

An AESI is an AE of scientific and medical interest specific to understanding of the IP and may require close monitoring and collection of additional information by the investigator. An AESI may be serious or nonserious.

The rapid reporting of AESIs allows ongoing surveillance of these events in order to characterize and understand them in association with the use of this IP.

The following AESIs will be particularly monitored in this trial:

- Hypersensitivity reaction, including anaphylaxis.
- Severe viral infection/reactivation (CTCAE Grade 3 or higher).
- Opportunistic infection.
- Malignancy (except non-melanoma skin cancer).

8.6.5 Classification of an Adverse Event

8.6.5.1 Relationship to Trial Treatment

The investigator is required to provide an assessment of the relationship of AEs and SAEs to the IP. An event will be considered "not related" to use of IP if any of the following are met:

- An unreasonable temporal relationship between administration of the IP and the onset of the event (eg, the event occurred either before, or too long after, administration of the IP for it to be considered IP related).
- A causal relationship between the IP and the event is biologically implausible (eg, death as a passenger in an automobile accident).
- A clearly more likely alternative explanation for the event is present (eg, typical adverse reaction to a concomitant drug and/or typical disease-related event).

Individual AE/SAE reports will be considered "related" to use of the IP if the "not related" criteria are not met.

"Related" implies that the event is considered to be "associated with the use of the drug" meaning that there is "a reasonable possibility" that the event may have been caused by the IP (ie, there are facts, evidence, or arguments to suggest possible causation).

8.6.5.2 Adverse Event Severity

The guidelines outlined in CTCAE v5.0 will be used for assessing the severity or intensity of the

event. The general guidelines for assessing the AE grade are provided in Table 5.

 Table 5: CTCAE v5.0 General Guidelines

Description
Mild; asymptomatic or mild symptoms; clinical or diagnostic observations only; intervention not indicated.
Moderate; minimal, local, or noninvasive intervention indicated; limiting age-appropriate instrumental ADL ^a .
Severe or medically significant but not immediately life-threatening; hospitalization or prolongation of hospitalization indicated; disabling; limiting self-care ADL ^b .
Life-threatening consequences; urgent intervention indicated.
Death related to AE.

Abbreviations: ADL, activities of daily living; AE, adverse event; CTCAE, Common Terminology for Adverse Events.

The CTCAE v5.0 is dated to 27 NOV 2017.

^a Instrumental ADL refers to preparing meals, shopping for groceries or clothes, using the telephone, managing money, etc.

^b Self-care ADL refers to bathing, dressing, and undressing, feeding self, using the toilet, taking medications, and not bedridden.

8.6.5.3 Expectedness

Horizon Therapeutics Ireland DAC will assess the expectedness of each SAE in relation to the IP.

8.6.6 Time Period and Frequency for Event Assessment and Follow-Up

The occurrence of an AE or SAE may come to the attention of trial personnel during trial visits and interviews of a trial participant presenting for medical care, or upon review by a trial monitor.

All AEs, including local and systemic reactions, will be captured on the appropriate eCRF. Information to be collected includes event description, date of onset, clinician's assessment of severity, relationship to IP (assessed only by those with the training and authority to make a diagnosis), and date of resolution/stabilization of the event. All AEs occurring while on trial must be documented appropriately regardless of relationship.

Trial site personnel will note the occurrence and nature of each participant's medical condition(s) present prior to the informed consent signature in the appropriate section of the source document and eCRF. During the trial, site personnel will note any change in the condition(s) and the occurrence and nature of any AE.

Any medical condition that is present prior to informed consent signature will be considered as part of medical history and not reported as an AE. However, if the trial participant's condition deteriorates after the consent signature, it will be recorded as an AE.

Should a participant experience an AE at any time after the informed consent signature until the end of participation in the trial, the event will be recorded as an AE in the source document and eCRF. Any SAE related to the trial participation (e.g., screening procedure) will be recorded in

the source document and eCRF from the time consent is given to participate in the trial until the end of participation in the trial.

The investigator is responsible for appropriate medical care of participants during the trial. The investigator also remains responsible for following through with an appropriate health care option for all AEs that are ongoing at the end of the trial. The participant should be followed until the event is resolved or stable. If an AE is ongoing at the end of trial, the follow-up duration is left to the discretion of the investigator. Follow-up frequency will be performed at the discretion of the investigator.

Whenever possible, clinically significant abnormal laboratory results are to be reported using the diagnostic that resulted in the clinically significant abnormal laboratory results and not the actual abnormal test.

8.6.7 Adverse Event Reporting

Investigators are responsible for monitoring the safety of participants who are participating in this trial and for alerting the sponsor to any event that seems unusual, even if this event may be considered an unanticipated benefit to the participant.

8.6.8 Serious Adverse Event Reporting

Horizon Therapeutics Ireland DAC will be the pharmacovigilance unit responsible for the overall pharmacovigilance process for this trial. All SAEs, related to the experimental treatment or not, occurring during the course of the trial must be reported by entering the information into the eCRF within 24 hours of knowledge of the occurrence (this refers to any AE that meets one or more of the aforementioned serious criteria). The SAE reporting period ends at the end of the follow-up period or if the participant begins an alternative therapy.

If unable to access the eCRF, the event must be reported by submitting the completed SAE form to the following e-mail address (faxing can also be done as a second option in case e-mailing is not possible) within 24 hours after becoming aware that a participant has experienced an SAE.

Safety Contact Information: Horizon Therapeutics E-mail: [contact] US [contact]

The pharmacovigilance unit will inform the medical monitor, the sponsor, and Innovaderm within 1 business day of awareness of a new SAE. The pharmacovigilance unit will process and evaluate all SAEs as soon as the reports are received. For each SAE received, the pharmacovigilance unit, in consultation with the Sponsor if needed, will make a determination as to whether the criteria for expedited reporting to relevant regulatory authorities have been met.

The expedited reporting of relevant safety information to concerned regulatory agencies and ethic committees will be performed in accordance with local laws and regulations and will be defined in the Safety Management Plan.

The trial sponsor will be responsible for notifying the Food and Drug Administration (FDA) of any unexpected fatal or life-threatening suspected adverse reactions as soon as possible, but in no case later than 7 calendar days after the sponsor's initial receipt of the information. In addition, the sponsor must notify the FDA and all participating investigators in an Investigational New Drug (IND) safety report of potential serious risks, from clinical trials or any other source, as soon as possible, but in no case later than 15 calendar days after the sponsor determines that the information qualifies for reporting.

8.6.9 Pregnancy Reporting

If a female participant becomes pregnant during the trial or up to 6 months after the last IP administration, whichever is longer, the participant should inform the trial site as soon as possible. Upon confirmation of the pregnancy, the female participant will be discontinued from the trial. If a female partner of a male participant becomes pregnant up to 6 months after the last IP administration of the male subject, the participant should inform the trial site as soon as possible. The investigator must complete a trial-specific pregnancy form upon confirmation of a pregnancy and send it to the pharmacovigilance unit within 24 hours of confirmation of the pregnancy (contact information to be used is the same as for SAE reporting). The pharmacovigilance unit will report all cases of pregnancy to the medical monitor, the sponsor, and Innovaderm in a timely manner. Pregnancy is not itself an AE or SAE; however, maternal/fetal complications or abnormalities will be recorded as AEs or SAEs, as appropriate. The investigator will follow the pregnancy until completion or until pregnancy termination and, in the case of a live-born offspring, to 1 month of age in that infant. The investigator will notify the pharmacovigilance unit and Innovaderm of the outcome as a follow-up to the initial pregnancy form. All pregnancies should be reported to the sponsor and, when applicable, to the ethics committee.

8.6.10 Overdose

Investigational product overdose is any accidental or intentional use of IP in an amount higher than the dose indicated per protocol for a given participant. Trial treatment compliance (see Section 6.3.2) should be reviewed to detect potential instances of overdose (intentional or accidental).

Any IP overdose during the trial should be recorded on the source document and eCRF. In the event of overdose, the participant should be closely monitored for any potential AEs. All AEs associated with an overdose should be entered on the Adverse Event eCRF and reported using the procedures detailed in Section 8.6.8, Serious Adverse Events Reporting, even if the events do not meet seriousness criteria. If the AE associated with an overdose does not meet seriousness criteria, it must still be reported using the SAEs reporting procedures and in an expedited manner but should be noted as non-serious on the form and the Adverse Event eCRF. The excess quantity and duration of the overdose should be recorded.

9 STATISTICAL CONSIDERATIONS

9.1 Sample Size Determination

A total of up to 30 participants will receive daxdilimab in the trial. The sample size was determined by the need to evaluate potential efficacy, safety and tolerability, and PK/PD. No formal power calculation was performed.

The mean percent reduction from baseline in SALT score was 58% in 4 mg group at Week 36 in Eli Lilly's phase 2 AA trial $(n=28)^{25}$. The lower bound of the 95% confidence interval was about 42%. With 30 participants, if we observe a mean percent reduction from baseline in SALT score of 58% at Week 24, there is about 98% confidence that the mean percent reduction from baseline is at least 42%. The estimated probability that true mean percent reduction from baseline in SALT score is above a cutoff for an observed mean is provided in Table 6.

Table 6: Probability that true mean percent reduction from baseline in SALT score is above a cutoff for an observed mean.

	Observed	Probability	that mean is		
n	Mean %reduction	≥35%	≥42%	$\geq 45\%$	
30	50%	0.97	0.85	0.74	
	55%	>0.99	0.95	0.90	
	58%	>0.99	0.98	0.95	

The proportion of patients achieving SALT ≤ 20 at Week 36 in 4 mg group was 33% and 35% in two Eli Lilly's phase 3 AA trials. The lower bound of the 95% confidence interval was about 27%. The estimated probability that true proportion of participants achieving SALT ≤ 20 is above 27% and other cutoffs for an observed response rate is provided in Table 7.

Table 7: Probability that true proportion of participants achieving SALT ≤20 is above a
cutoff for an observed response rate.

	Observed	Probability	that response rate is	
n	response rate	≥20%	≥25%	≥27%
30	9 (30%)	0.87	0.67	0.58
	11(36.7%)	0.97	0.89	0.84
	12(40%)	0.99	0.95	0.92
	13(43.3%)	0.99	0.98	0.96
	15(50%)	0.99	0.99	0.99

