9.3.2 Efficacy Analyses

9.3.2.1 Analysis of the Primary Efficacy Endpoint

The primary efficacy endpoint of percent change from baseline in SALT score at Week 24 will be summarized using descriptive statistics. A 2-sided 95% confidence interval will be calculated for the mean.

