9.3.7 Planned Analyses

The primary analysis will be performed when the last participant has completed Week 24 or withdraws prior to the scheduled Week 24 visit. All available data at the time of the data cut-off (including data collected after Week 24) will be included in the primary analysis.

The final analysis will be performed when all participants have completed trial.

Page 60 of 70

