2.3 Sample Size

A total of up to 30 participants will receive daxdilimab in the trial. The sample size was determined by the need to evaluate potential efficacy, safety and tolerability, and PK/PD. No formal power calculation was performed.

The mean percent reduction from baseline in SALT score was 58% in 4 mg group at Week 36 in Eli Lilly's phase 2 AA trial (n=28) (King B, Ko J, Forman S, et al., 2021). The lower bound of the 95% confidence interval was about 42%. With 30 participants, if we observe a mean percent reduction from baseline in SALT score of 58% at Week 24, there is about 98% confidence that the mean percent reduction from baseline is at least 42%. The estimated confidence level that true mean percent reduction from baseline in SALT score is above a cutoff for an observed mean is provided in Table 2.

Table 2Confidence level that true mean percent reduction from baseline in SALT
score is above a cutoff for an observed mean

	Observed		Confidence that mean is	5
n	Mean % reduction	≥35%	≥42%	≥45%
30	50%	0.97	0.85	0.74
	55%	>0.99	0.95	0.90
	58%	>0.99	0.98	0.95

The proportion of patients achieving SALT ≤ 20 at Week 36 in 4 mg group was 33% and 35% in two Eli Lilly's phase 3 AA trials. The lower bound of the 95% confidence interval was about 27%. The estimated confidence level that true proportion of participants achieving SALT ≤ 20 is above 27% and other cutoffs for an observed response rate is provided in Table 3.

Table 3	Confidence level that true proportion of participants achieving SALT ≤ 20
	is above a cutoff for an observed response rate.

	Observed	Confidence that response rate is		
n	response rate	≥20%	≥25%	≥27%
30	9 (30%)	0.87	0.67	0.58
	11(36.7%)	0.97	0.89	0.84
	12(40%)	0.99	0.95	0.92
	13(43.3%)	0.99	0.98	0.96
	15(50%)	0.99	0.99	0.99

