4.7.2 Secondary Efficacy Endpoints and Analyses

4.7.2.1 Secondary Efficacy Endpoints

The secondary efficacy endpoints are as follows:

- Percent change from baseline in SALT score at Weeks 12-20, 28-36, and Weeks 40-48.
- Proportion of participants who achieve ≥ 50% reduction in SALT from baseline at Weeks 12-36 and Weeks 40-48.
- Proportion of participants with absolute SALT score $\leq 10, 20, 30, 50$ at Weeks 12-36 and Weeks 40-48.

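### Does it matter that the Week 24 precision statement borrows a Week 36 benchmark from another drug and does not print its SD?

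*Protocol*

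**What the plan says.** The sample-size sections of the two documents (Protocol 9.1, SAP 2.3) carry the same argument.

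- The benchmark is introduced with its visit: "The mean percent reduction from baseline in SALT score was 58% in 4 mg group at Week 36", from another sponsor's phase 2 alopecia areata trial with n=28. The source is cited, and its title in the reference list identifies an oral JAK inhibitor.
- The cutoff comes next: "The lower bound of the 95% confidence interval was about 42" percent.
- The figures are then applied to this trial. Protocol: "With 30 participants, if we observe a mean percent reduction from baseline in SALT score of 58% at Week 24". SAP: "if we observe a mean percent reduction from baseline in SALT score of 58% at Week 24". The stated result is about 98% confidence that the mean reduction is at least 42%.
- Protocol Table 6 and SAP Table 2 extend this to observed means of 50%, 55% and 58% against cutoffs of 35%, 42% and 45%.
- On power, Protocol 9.1 says: "No formal power calculation was performed".

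The primary analysis is descriptive. Protocol 9.3.2.1 specifies: "A 2-sided 95% confidence interval will be calculated for the mean". SAP 4.7.1.2 plans the same interval. On timing, Protocol 9.3.7 says: "The primary analysis will be performed when the last participant has completed Week 24" or has withdrawn before that visit. Week 36 is covered separately as a secondary time point in SAP 4.7.2.1: "Percent change from baseline in SALT score at Weeks 12-20, 28-36, and Weeks 40-48".

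**The concern.** Two things stand out on first reading.

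First, the visits do not match. The 58% and 42% were observed at Week 36 on another drug, and the next sentence sets this trial's Week 24 mean against them without comment. If response is still rising between Weeks 24 and 36, a Week 36 figure is a demanding reference for a Week 24 mean. The documents give no time course, so the reader cannot judge this.

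Second, the tables cannot be calculated without an SD, and neither document gives one, or its source, or the formula. This is the only precision statement for the mean that forms the primary endpoint, and the expected width of the planned 95% interval is not printed either.

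If the SD were badly chosen, or the 98% wrong, readers could think that 30 participants support a firmer statement about the Week 24 mean than they do. In a single-arm proof-of-concept trial, that impression is most of what a sample-size section conveys.

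**Working it through.** **Inputs (Protocol 9.1, SAP 2.3).** Comparator mean 58%, lower 95% bound about 42%, comparator n=28, planned n=30. No SD is given.

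**Step 1. SD implied by the comparator interval.**
SE = (58 − 42)/quantile; SD = SE × √28.
- t with 27 df: 16/2.052 = 7.80; SD = 41.3.
- Normal: 16/1.96 = 8.16; SD = 43.2.

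**Step 2. Reproduce the plan's table.**
Confidence = F((observed mean − cutoff)/(SD/√30)), where F is the t distribution with 29 df or the normal. The SE at n=30 is 41.3/√30 = 7.54 or 43.2/√30 = 7.89.

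| Observed mean | Cutoff | Printed | t, SD 41.3 | Normal, SD 43.2 |
|---|---|---|---|---|
| 50% | 35% | 0.97 | 0.972 | 0.971 |
| 50% | 42% | 0.85 | 0.852 | 0.845 |
| 50% | 45% | 0.74 | 0.744 | 0.737 |
| 55% | 35% | >0.99 | 0.994 | 0.994 |
| 55% | 42% | 0.95 | 0.953 | 0.950 |
| 55% | 45% | 0.90 | 0.903 | 0.898 |
| 58% | 35% | >0.99 | 0.998 | 0.998 |
| 58% | 42% | 0.98 | 0.979 | 0.979 |
| 58% | 45% | 0.95 | 0.953 | 0.950 |

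With t, all nine cells round to the printed values. With the normal, eight do; the exception is 0.8448 (50% against 42%), just under the printed 0.85.

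**Step 3. Which SDs fit every cell?** A search over SD gives 41.1 to 42.4 (t) or 42.0 to 43.2 (normal). The comparator-implied value lies inside the t range and at the upper edge of the normal range. So the SD was very probably taken from the Week 36 interval, although the documents do not say so.

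**Step 4. How much depends on that SD?** The documents give no Week 24 SD, so 30 to 50 is an assumed range. Half-width = t(0.975, 29) × SD/√30.

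| SD | 95% CI half-width (points) | Confidence of at least 42% when 58% is observed (t, 29 df) |
|---|---|---|
| 30 | 11.2 | 0.997 |
| 41.3 | 15.4 | 0.979 |
| 43.2 | 16.1 | 0.974 |
| 50 | 18.7 | 0.955 |

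**Step 5. Is the interval width really absent?** Not in substance. About 98% one-sided confidence of exceeding 42% at an observed 58% puts the lower limit of a two-sided 95% interval close to 42%, which is a half-width of about 58 − 42 = 16 points. This agrees with the 15.4 to 16.1 in Step 4.

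**Step 6. Does anything use 42% or the planning SD later?** Protocol 9.3.2.1 and SAP 4.7.1.2 report the mean with its own 95% interval, and Protocol 9.3.1 and SAP 4.1 add the observed SD. There is no hypothesis test, success threshold or stopping rule tied to 42%.

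**The case for a change.** The best case for a change runs as follows. A table that depends on an SD should print that SD. The reader should not have to invert a competitor's confidence interval to check it, and an inferred source is weaker than a stated one. A sample-size section built around a confidence interval should give the expected half-width. A Week 36 active-drug figure set against a Week 24 mean invites a cross-trial reading at the primary analysis with no caution attached, although this trial has its own Week 36 secondary endpoints for a same-visit comparison. Two or three sentences would deal with all of it.

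Part of this stands. The SD and method are not printed, and the step from Week 36 to Week 24 is not explained. A short clarifying sentence would be good practice.

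The rest does not support a change. The Week 36 origin of 58% and 42% is already on the page, with the dose group, sample size and citation, and Week 24 is named in the sentence that applies them, so a reader can see the mismatch. The numbers needed to recover the SD are printed, and Step 2 shows that they suffice. The table is not tied to a single cutoff: it also gives 35% and 45%. A pointer to a Week 36 comparison would add nothing to the analysis, because those endpoints are already planned. Such a comparison would still be uncontrolled and across trials, and Week 36 data may be incomplete at the primary cut-off.

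**Conclusion.** No change to the plan is needed. This is missing explanatory detail around an illustration that is correct at its implied SD. The 98% figure reproduces (0.979), as do the other eight cells with t and an SD of 41.3 points. The expected half-width of the Week 24 interval is about 15 to 16 points. For an assumed SD of 30 to 50 the half-width runs from about 11 to 19 points and the 98% from 0.997 to 0.955, so the message of the illustration holds.

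The carry-over from Week 36 to Week 24 affects only how demanding the reference is. If response were still rising after Week 24, it would make 42% a stricter mark for daxdilimab. The documents do not settle whether response does rise.

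The conclusion rests on three points. The analysis is descriptive and no rule uses 42%. The reported interval will come from the trial's own data. The comparator-derived SD is an inference from close numerical agreement, not something the documents state. Adding the SD, its source and a remark on the visit difference is optional editing; it would alter no estimate, interval or decision.
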